## List of Abbreviations

ap	acellular pertussis (lower content)
aP	acellular pertussis (higher content)
AE	adverse event
AR	adverse reaction
CDM	Clinical Data Management
CLC	Clinical Logistics Coordinator
CMI	cell mediated immunity
CRA	Clinical Research Associate
eCRF	electronic case report form
CTA	clinical trial agreement
CTL	Clinical Team Leader
d	reduced diphtheria toxoid
D	day
DC	diary card
EDC	electronic data capture
ELISA	enzyme linked immunosorbent assay
ELS	extensive limb swelling
ESDR	early safety data review
FAS	full analysis set
FHA	filamentous hemagglutinin
FIM	fimbriae types 2 and 3
FVFS	first visit, first subject
FVLS	first visit, last subject
GCI	Global Clinical Immunology
GCP	Good Clinical Practice
GPV	Global PharmacoVigilance
IATA	International Air Transport Association
ICF	informed consent form
ICH	International Conference on Harmonisation
IEC	Independent Ethics Committee
IND	investigational new drug (application)
IRB	Institutional Review Board
IVRS	interactive voice response system
IWRS	interactive web response system
LCLS	last contact, last subject

---

LLT	[MedDRA] lowest level term
LLOQ	lower limit of quantification
MA	memory aid
MAAE	medically-attended adverse events
MedDRA	Medical Dictionary for Regulatory Activities
mL	milliliter
OG	Operating Guidelines
PPAS	per-protocol analysis set
PRN	pertactin
PSO	Product Safety Officer
PT	pertussis toxoid
RMO	Responsible Medical Officer
SAE	serious adverse event
SafAS	safety analysis set
SMT	safety management team
T	tetanus toxoid
TMF	trial master file
ULOQ	upper limit of quantification
US	United States
V	Visit
WHO	World Health Organization

# 1 Introduction

## 1.1 Background

### Tetanus

Tetanus is an acute and often-fatal infection caused by an extremely potent neurotoxin produced by *Clostridium tetani*, which is most commonly found in soil (1). The disease is characterized by severe, painful muscle contractions, accompanied by hypersensitivity, hyperreflexia, and increased autonomic stimulation of the affected body part(s). Complications associated with tetanus include laryngospasms, spinal and long bone fractures, and hypertension (2). Tetanus occurs sporadically worldwide, but it is uncommon in developed countries, mainly because of immunization and hygienic precautions taken in the management of wound and surgical procedures.

### Diphtheria

Diphtheria is an acute infection caused by *Corynebacterium diphtheriae*. The main site of infection is the upper respiratory tract, characterized by a patch of grayish pseudomembrane surrounded by inflammation. Complications associated with diphtheria include airway obstruction, myocarditis, and paralysis. The case-fatality rate runs as high as 30–95%, particularly in the elderly, despite modern medical care (3).

### Pertussis

Pertussis (whooping cough) is a highly contagious infectious disease of the respiratory tract caused by *Bordetella pertussis*. The illness is characterized by severe coughing spasms, which may or may not be associated with the classic inspiratory whoop. Although pertussis is most severe and complications are most frequent in children less than one year of age, pertussis can affect persons of any age (4). Antimicrobial therapy is effective in eradicating the organism from the respiratory tract but does not alter the progression of the disease unless given in the early stage when pertussis is rarely suspected; therefore, control of the disease has been based on vaccine prophylaxis (5).

## 1.2 Background of the Investigational Product

The proposed updated Tdap vaccine, under evaluation in Study ADC01, will include the same antigenic components as Adacel®. The investigational formulations differ from Adacel® primarily in the amount per dose of pertussis antigens pertussis toxoid (PT), pertactin (PRN), and fimbriae types 2 & 3 (FIM), and/or in the [REDACTED]. The selection of Tdap formulations to be evaluated in Study ADC01 was based on safety and immunogenicity data obtained with varying antigen concentrations in clinical trials conducted in different age groups, as well as data from a range of in vitro formulation and process development studies and animal immunogenicity evaluations.

## 1.3 Potential Benefits and Risks

### 1.3.1 Potential Benefits to Subjects

Subjects in all groups will be vaccinated with either one of the four investigational Tdap formulations or a licensed Tdap vaccine (Adacel® or BOOSTRIX®) and will likely gain benefit against infectious disease through boosting of their immunity to diphtheria, tetanus and pertussis.

### 1.3.2 Potential Risks to Subjects

Based on safety data from previous trials with similar products, potential risks of the study vaccines are limited to the usual injection site reactions expected following any injectable vaccine such as pain, redness and swelling. Fever may also occur but is generally mild in intensity. Extensive Limb Swelling (ELS) has been reported in a small proportion of individuals following vaccination with acellular pertussis vaccines and may be more common following booster doses. All these reactions resolve spontaneously, usually within a few days after vaccination.

As with any vaccine, investigational Tdap vaccine formulations may not protect 100% of individuals against the diseases they are designed to prevent.

The risks associated with blood drawing include injection site pain, bruising, and (rarely) fainting or infection.

Tdap is contraindicated in persons with known systemic hypersensitivity to any of their components or a history of life-threatening reaction to the vaccine or to a vaccine containing the same substances. Because of uncertainty as to which vaccine component may be responsible, no further vaccination with the diphtheria, tetanus, or pertussis components found in Tdap should be carried out.

Please see the Investigator Brochure for complete descriptions of the potential risks associated with Tdap vaccines.

## 1.4 Rationale for the Trial

The overall goal of this Phase I/II Study is to select a formulation for further clinical development of SP0173 (Tetanus Toxoid [T], Reduced Diphtheria Toxoid [d] and Acellular Pertussis Vaccine Adsorbed [ap]) as a combination pertussis vaccine formulation (Tdap) to boost immunity towards the targeted diseases in individuals  $\geq 10$  years of age.

In Study ADC01, SP0173 antibody GMCs will be evaluated in 1 of 2 ways, depending on subject age. In subjects  $< 65$  years of age, SP0173 antibody GMCs for T, d, and pertussis antigens will be compared with Adacel®. In subjects  $\geq 65$  years of age SP0173 antibody GMCs for T and d will be compared with Adacel®, whereas antibody GMCs for pertussis antigens will be compared with historical responses from the Sweden I (for filamentous hemagglutinin [FHA], FIM, and PRN) and M5A10 (for PT) (6) studies. The immunogenicity objectives of Study ADC01 are observational and therefore the study is not powered to detect statistically significant differences in antibody responses between candidate formulations or to assess non-inferiority to historical controls.

Collectively, safety and immunogenicity data will be essential determinants of the suitability of a candidate vaccine formulation for advancement to Phase III clinical development.

## 2 Trial Objectives

### 2.1 Observational Objectives

#### *Safety/Reactogenicity*

- To describe the safety profile of each SP0173 investigational formulation.

#### *Immunogenicity*

- To describe the immunogenicity of each SP0173 investigational formulation.

The endpoints for the observational objectives are presented in [Section 9.3.1.2](#) and [Section 9.3.2.1](#).

## 3 Investigators and Trial Organization

This study will be conducted in approximately 20 centers in the US. Details of the study centers and the Investigators at each center are provided in the “List of Investigators and Centers Involved in the Trial” document.

The safety of the investigational product will be continuously monitored by the Sponsor and will include 3 types of surveillance:

- *Ongoing safety surveillance* of SAE.
- *Periodic safety surveillance* (during enrollment and safety data collection for each of the 2 sets of age cohorts: adults followed by adolescents/older adults) [REDACTED]
- *Early Safety data review (ESDR)*, during which enrollment in the study (between age cohorts) will be paused. [REDACTED]

Immunogenicity testing will all be performed at the Sanofi Pasteur Global Clinical Immunogenicity (GCI) laboratories in Swiftwater, PA, USA.

The Sponsor's Responsible Medical Officer (the person authorized to sign this protocol and any amendments on behalf of the Sponsor) is [REDACTED], [REDACTED], Clinical Team Leader (CTL) or such delegate as may be identified in her absence.

## 4 Independent Ethics Committee/Institutional Review Board

Before the investigational product can be shipped to the investigational site and before the inclusion of the first subject, this protocol, the informed consent form (ICF), subject recruitment procedures, and any other written information to be provided to subjects must be approved by, and/or receive favorable opinion from, the appropriate Independent Ethics Committee (IEC) or Institutional Review Board (IRB).

In accordance with Good Clinical Practice (GCP) and local regulations, each Investigator and/or the Sponsor are responsible for obtaining this approval and/or favorable opinion before the start of the trial. If the protocol is subsequently amended, approval must be re-obtained for each substantial amendment. Copies of these approvals, along with information on the type, version number, and date of document, and the date of approval, must be forwarded by the Investigator to the Sponsor together with the composition of the IEC/IRB (the names and qualifications of the members attending and voting at the meetings).

The Investigator will submit written summaries of the status of the trial to the IEC/IRB annually, or more frequently if requested. All SAEs occurring during the trial that are related to vaccination will be reported by the Investigator to the IEC/IRB, according to the IEC/IRB policy.

## 5 Investigational Plan

### 5.1 Description of the Overall Trial Design and Plan

#### 5.1.1 Trial Design

This will be a Phase I/II, randomized, modified double-blinded, multi-center, active comparator, multiple-formulation, dose ranging, step-down study to assess the safety and immunogenicity of SP0173 in healthy adolescents, adults, and older adults conducted in the US.

Subjects' age groups are defined as follows:

- Adolescents: age 10–18 years
- Adults: age 19–64 years
- Older Adults: age  $\geq$  65 years

The planned sample size is 1350 subjects (450 subjects per age group). Within each age group subjects will be randomized in equal proportion to receive a single dose of SP0173 (1 of 4 formulations), Adacel®, or BOOSTRIX® (Table 5.1).

**Table 5.1: Study groups and vaccine formulations**

Study Group	Vaccine Formulation	Age Group		Vaccine Components				Other
		Adolescent	Adult	PT	PRN	FIM	FHA	
[REDACTED]	[REDACTED]	[REDACTED]	[REDACTED]	[REDACTED]	[REDACTED]	[REDACTED]	[REDACTED]	[REDACTED]
[REDACTED]	[REDACTED]	[REDACTED]	[REDACTED]	[REDACTED]	[REDACTED]	[REDACTED]	[REDACTED]	[REDACTED]
[REDACTED]	[REDACTED]	[REDACTED]	[REDACTED]	[REDACTED]	[REDACTED]	[REDACTED]	[REDACTED]	[REDACTED]
[REDACTED]	[REDACTED]	[REDACTED]	[REDACTED]	[REDACTED]	[REDACTED]	[REDACTED]	[REDACTED]	[REDACTED]
[REDACTED]	[REDACTED]	[REDACTED]	[REDACTED]	[REDACTED]	[REDACTED]	[REDACTED]	[REDACTED]	[REDACTED]
[REDACTED]	[REDACTED]	[REDACTED]	[REDACTED]	[REDACTED]	[REDACTED]	[REDACTED]	[REDACTED]	[REDACTED]

Subjects will be monitored for immediate unsolicited systemic AEs for 30 minutes after vaccination. Solicited reactions (injection site and systemic) will be collected from Day (D)0 to D7 post-vaccination. Unsolicited AEs will be collected from V01 (D0) to V02 (D30-D44) and SAEs will be collected throughout the study period from D0 through D180 after vaccination.

Medically-attended adverse events (MAAEs) will be collected throughout the study from V01(D0) to V02(D30-D44) as part of the collection of unsolicited AE information and from V02 to the end of the 6-month follow-up (D180) as MAAEs. An MAAE that occurs within the study period but meets the definition of an SAE should be reported as an SAE.

All subjects will be asked to provide a blood sample for immunogenicity assessment at baseline (pre-vaccination at V01) and at V02. A subset of subjects (36 adolescents, 60 adults and 60 older adults) enrolled in all groups will provide an additional pre- and post-vaccination blood sample for exploratory testing of parameters of cell-mediated immunity (CMI). The results of that testing will be described in a separate report.

**5.1.2 Justification of the Trial Design**

The proposed Phase I/II study, ADC01, will be the first trial in humans to evaluate the different formulations of SP0173 (low-, middle- and high-dose) when adjuvanted to either [REDACTED] or [REDACTED] and administered to adolescent, adults and older adults, i.e. the key target age groups where administration of a tetanus, diphtheria and pertussis vaccine is recommended by the Advisory Committee on Immunization Practices in the US. The dose of pertussis antigens to be explored in all age groups varies for the PT, PRN and FIM components and is the same in all formulations for the FHA component.

The selection of investigational Tdap formulations to be evaluated in ADC01 was based on safety and immunogenicity data obtained with varying antigen concentrations in clinical trials conducted in different age groups, as well as data from a range of *in vitro* formulation and process

development studies and animal immunogenicity evaluations. The immunogenicity of each formulation is enhanced by the presence of an [REDACTED].

As a safety precaution, Study ADC01 will employ a step-down approach for enrollment: adult subjects (age 19–64 years) will be enrolled and vaccinated, and an internal review of safety data collected through D30 after injection will be conducted; an acceptable review of safety data and an acceptable safety profile based on prospectively defined criteria will be required before concurrent enrollment of adolescent (age 10–18 years) and older adult subjects (age  $\geq$  65 years).

### 5.1.3 Trial Plan

Eligible subjects will be identified and enrolled at each research center. Initially, enrollment will be restricted to the subjects in the adult age group (19–64 years of age). Enrollment of adolescent and older adult subjects is planned subsequent to a satisfactory review of safety data from V01 through V02 post-vaccination for the adult age group.

Each subject and/or subjects' parent/guardian must sign and date the ICF (and assent form for subjects under the age of legal majority [according to state regulation]) before any procedure or treatment associated with the study is performed.

Subjects will receive one injection of either SP0173 vaccine, Adacel®, or BOOSTRIX® on D0. Each subject will be asked to provide a blood sample (10–20 mL/bleeda) to be collected before vaccine injection at V01 (D0) and at V02 (30 days [ $\pm$  14 daysb] after injection).

All subjects and/or subjects' parent/guardian will be asked to record solicited injection site reactions and solicited systemic reactions that occur for 7 days after the injection and unsolicited AEs that occur from V01(D0) through V02 (D30). SAEs will be collected throughout the study period from D0 through D180 after vaccination. MAAEs will be collected throughout the study from V01 through V02 (as part of the collection of unsolicited AEs) and from V02 through D180 (as MAAEs).

### 5.1.4 Visit Procedures

#### V01 (D0): Inclusion, Randomization, Applicable Blood Sample, and Vaccination

- 1) Give the subject or subject's parent/guardian information about the study.
- 2) Obtain informed consent and assent (for subjects under the legal age of majority [according to state regulations]) and answer any questions to ensure that the subjects and/or subject's parent/guardian have been informed of all aspects of the trial that are relevant to their decision to participate. Document the informed consent process in the subject's record.

---

a Most subjects will provide approximately 10 mL of blood at each blood draw. Subjects enrolled in the CMI subset will provide an additional 10 mL of blood pre- and post-vaccination.

b For subjects in the CMI subset, the V02 window will be between Day 30 and Day 37.

- 3) Date and sign the ICF (and assent form for subjects under the legal age of majority [according to state regulations]) after it has been signed and dated by the subject or subject's parent/guardian. Retain the original and give a signed copy to the subject or subject's parent/guardian.
- 4) Check inclusion and exclusion criteria for eligibility.
- 5) Collect demographic information.
- 6) For women of childbearing potentiala, obtain a urine pregnancy test.
- 7) Obtain verbal medical and vaccination history about the subject (including relevant prior and concomitant therapy).
- 8) Perform and document a limited physical examination per standard site-specific immunization practices. If a routine physical examination was performed at the same clinical site no more than 30 days before V01, verify and record any changes in the subject's health status and update with a signature, noting review by someone delegated to perform a physical examination. Measure and record temperature. If the temperature is  $\geq 100.4^{\circ}\text{F}$ , postpone vaccinations until the condition is resolved.
- 9) Call the IVRS/IWRS for assignment of the subject number, randomization to study group, and allocation of the product to be administered (should be performed by the unblinded administrator).
- 10) Obtain pre-vaccination blood sample (see [Section 7.1](#) for detailed instructions regarding the handling of blood samples).
- 11) Instruct the subject or subject's parent/guardian how to perform and record the arm circumference measurements. The subject or subject's parent/guardian will be requested, under the supervision of the study staff, to perform the baseline measurement of both arms. Record the circumference of both arms in the source document and transcribe that of the vaccinated arm in the subject's DC.
- 12) Administer the study or control vaccine intramuscularly in the deltoid region of the arm.
- 13) Keep the subject under observation for 30 minutes, and record any adverse reaction in the source documents and electronic case report form (eCRF).
- 14) Provide the DC to the subject or subject's parent/guardian and ask them to record in it solicited injection site and systemic reactions for D0 to D7. Ask them to use the DC to record any unsolicited AEs (from V01 to V02) and concomitant medications. MAAEs that occur from V01 to V02 will be recorded as unsolicited AEs on the DC as part of the unsolicited AEs collected for this post-vaccination period. Provide appropriate training including ruler, measuring tapes, digital thermometer, and instructions for use.

---

a To be considered of non-childbearing potential, a female must be pre-menarche or post-menopausal for at least 1 year, surgically sterile, or using an effective method of contraception, or abstinence from at least 4 weeks prior to vaccination until at least 4 weeks after vaccination.

- 15) Instruct the subject or subject's parent/guardian to expect a telephone contact on D8 post-vaccination to identify the occurrence of any SAE, Grade 3 solicited adverse reactions (including ELS) not yet reported and to remind him/her to complete the DC up to V02 and bring it back at V02. The date of the appointment for V02 will be confirmed.
- 16) If the subject develops a Grade 3 solicited injection site or systemic AE (see [Table 9.1](#) and [Table 9.2](#)), develop significant change in arm circumference (increased  $\geq 50$  mm from pre-vaccination measurement at baseline), or ELS which occur during the 7-day period after vaccination, the subject or subject's parent/guardian is required to contact the site immediately. The site staff must attempt for the subject to be seen at the study site within 24 hours to assess the extent of the reaction. In cases of Grade 3 injection site swelling or ELS, the subject (or parent/guardian) is to be instructed to take measurements of the vaccinated arm circumference, and record in the DC, until the swelling is resolved (See Operating Guidelines [OG] for details).
- 17) Set up an appointment for V02 (D30–D44) and instruct the subject or subject's parent/guardian to bring the DC to the visit to discuss the information entered with the study personnel.

*Note: For subjects in the CMI subset, the V02 window will be between D30 and D37*

- 18) Remind the subject or subject's parent/guardian to notify the site in case of an SAE.
- 19) Complete the relevant case report form (eCRF) pages for this visit.

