	
 
1) Subject is pregnant, or lactating, or of childbearing potential (to be considered of non-childbearing potential, a female must be pre-menarche or post-menopausal for at least 1 year, surgically sterile, or using an effective method of contraception or abstinence from at least 4 weeks prior to vaccination until at least 4 weeks after vaccination.)
 
2) Participation at the time of study enrollment (or in the 4 weeks preceding the study vaccination) or planned participation during the present study period in another clinical trial investigating a vaccine, drug, medical device, or medical procedure.
 
3) Received any vaccine in the 4 weeks preceding the trial vaccination or planned receipt of any vaccine between V01 and V02. For influenza vaccine only, defer if received in the 14-day period prior to enrollment or scheduled to receive in the 14-day period after enrollment.
 
4) Known or suspected receipt of a tetanus toxoid, reduced diphtheria toxoid, and acellular pertussis (Tdap) vaccine or Tdap-containing vaccine at any point in time, or receipt of a tetanus and diphtheria containing vaccine in the preceding 5 years.
 
5) Receipt of immune globulins, blood or blood-derived products in the past 3 months.
 
6) Known or suspected congenital or acquired immunodeficiency, immunosuppressive therapy such as anti-cancer chemotherapy or radiation therapy within the preceding 6 months, or long-term systemic corticosteroids therapy (prednisone or equivalent for more than 2 consecutive weeks within the past 3 months).
 
7) History of diphtheria, tetanus, or pertussis infection (confirmed either serologically or microbiologically).
 
8) Known or suspected systemic hypersensitivity to any of the vaccine components or history of life-threatening reaction to the study vaccine or a vaccine containing the same substances.
 
9) Laboratory-confirmed/self-reported thrombocytopenia or bleeding disorder contraindicating IM vaccination.
 
10) Bleeding disorder, or receipt of anticoagulants in the 3 weeks preceding inclusion, contraindicating IM vaccination
 
11) History of encephalopathy (e.g., coma, decreased level of consciousness, or prolonged seizures) not attributable to another identifiable cause within 7 days of administration of a previous dose of diphtheria and tetanus toxoids and pertussis (DTP), or diphtheria and tetanus toxoids and acellular pertussis (DTaP) vaccine
 
12) Deprived of freedom by an administrative or court order, or in an emergency setting, or hospitalized involuntarily.
 
13) Current alcohol abuse or drug addiction.
 
14) Chronic illness that, in the opinion of the investigator, is at a stage where it might interfere with trial conduct or completion.
 

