## Table of Study Procedures

Phase I/II Study, 2 Visits, 1 Vaccination, 2 Telephone Calls 2 Blood Samples, 180-Days Duration  
Per Subject

Visit (V)/Contact	Visit 1 (V01)	Telephone Contact 1 (TC1)	Visit 2 (V02)	Telephone Contact 2 (TC2)
Study timelines (days)	D0	D8	D30	D180
Time windows (days)		[+3 Days]	[+ 14 Days]*	[+14 days]
Informed consent form/Assent form (if applicable) †	X			
CMI informed consent addendum form, as applicable	X			
Inclusion/exclusion criteria	X			
Temperature	X			
Collection of demographic data	X			
Urine pregnancy test (if applicable) ‡	X			
Verbal medical and vaccination history	X			
Physical examination §	X			
Collection of Concomitant Therapy**	X			
Measure circumference of both arms ††	X			
Randomization/allocation of subject number	X			
Blood sampling (BL), approximately 10–20 mL ‡‡	BL1		BL2	
Vaccination	X			
Immediate surveillance (30 min)	X			
Diary card provided	X			
Telephone contact §§		X		
Diary card collected and reviewed			X	
Collection of solicited injection site and systemic reactions			X	
Recording of unsolicited AEs	D0 to V02			
Memory aid provided ***			X	
Recording of MAAEs †††			Visit 02 to TC2	
Recording of SAEs	To be reported at any time during the study			
Follow-up telephone call ‡‡‡				X
Completion of 6-month follow-up				X

---

\*For subjects in the CMI subset, the window will be [+ 7 Days].

†Age of majority to follow state regulations

‡For women of childbearing potential. The urine pregnancy test must be performed before vaccination. The pregnancy test must be negative for enrollment.

§Targeted physical examination based on medical history. Temperature needs to be measured and recorded in the source documents.

\*\*As specified in [Section 6.7](#).

††If the subject develops a Grade 3 solicited injection site (including ELS) or systemic reaction, the subject or subject's parent/guardian is required to contact the site immediately. The site must attempt for the subject to be seen at the study site within 24 hours to assess the extent of the reaction.

‡‡Collection of the baseline blood sample (BL1) before vaccination, approximately 10 mL. An additional 10 mL will be collected for the CMI subgroup at each time point.

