### 5.2.5 Exclusion Criteria

An individual fulfilling *any* of the following criteria is to be excluded from trial enrollment:

- 1) Subject is pregnant, or lactating, or of childbearing potential (to be considered of non-childbearing potential, a female must be pre-menarche or post-menopausal for at least 1 year, surgically sterile, or using an effective method of contraception or abstinence from at least 4 weeks prior to vaccination until at least 4 weeks after vaccinationd).
- 2) Participation at the time of study enrollment (or in the 4 weeks preceding the study vaccination) or planned participation during the present study period in another clinical trial investigating a vaccine, drug, medical device, or medical procedure.
- 3) Received any vaccine in the 4 weeks preceding the trial vaccination or planned receipt of any vaccine between V01 and V02. For influenza vaccine only, defer if received in the 14-day period prior to enrollment or scheduled to receive in the 14-day period after enrollment.
- 4) Known or suspected receipt of a tetanus toxoid, reduced diphtheria toxoid and acellular pertussis (Tdap) vaccine, or Tdap-containing vaccine at any point in time, or receipt of a tetanus and diphtheria-containing vaccine in the preceding 5 years.
- 5) Receipt of immune globulins, blood or blood-derived products in the past 3 months.

---

a “10 to 18 years” means from the day of the 10th birthday to the day before the 19th birthday

b “19 to 64 years” means from the day of the 19th birthday to the day before the 65th birthday

c “ $\geq 65$  years” means from the day of the 65th birthday or older

d For pre-menarche females, the young female subjects will declare by themselves if they have not yet started menstruation. If a young female subject reaches menarche during the study, then she is to be considered as a woman of childbearing potential from that time forward.

- 6) Known or suspected congenital or acquired immunodeficiency, immunosuppressive therapy such as anti-cancer chemotherapy or radiation therapy within the preceding 6 months, or long-term systemic corticosteroids therapy (prednisone or equivalent for more than 2 consecutive weeks within the past 3 months).
- 7) History of diphtheria, tetanus, or pertussis infection (confirmed either serologically or microbiologically).

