### 5.2.12 Follow-up and Reporting of Pregnancies

Pregnancy is an exclusion criterion for enrollment in this study, but a subject could potentially become pregnant during her participation. In case of pregnancy and if study vaccine has been administered, the subject will not be discontinued from the trial and will be followed for safety assessment (and may be followed for immunogenicity assessment, if applicable).

All pregnancy cases should be reported if they occurred during the study. To report the pregnancy case, the Investigator must fill out a Pregnancy Reporting Form in the electronic data capture (EDC) system and send it to the Sponsor within 1 month of identifying a pregnancy case.

Study staff must then maintain contact with the subject to obtain information about the outcome—i.e., details about the delivery and the newborn, or about pregnancy termination—and must update the electronic Pregnancy Reporting Form. This information should be provided to the Sponsor within 1 month of delivery.

Pregnancy itself is not considered an AE, but any complications during pregnancy are to be considered as AEs, and in some cases could be considered SAEs. Spontaneous abortions, fetal death, stillbirth, and congenital anomalies reported in the baby are always considered as SAEs, and the information should be provided to the Global Pharmacovigilance (GPV) Department regardless of when the SAE occurs (e.g., even after the end of the trial).

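### As worded, the V01 urine pregnancy test applies to no woman who can enrol, because the same definition that triggers the test also excludes her

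*Protocol*

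**What the plan says.** - **The test.** Protocol 5.1.4, V01 step 6, calls for a urine pregnancy test "For women of childbearing potential". The footnote to the Table of Study Procedures has the same restriction and adds: "The urine pregnancy test must be performed before vaccination. The pregnancy test must be negative for enrollment". SAP Table 3.2 repeats that footnote.
- **The definition attached to the test.** The step 6 footnote says who is not of childbearing potential. After pre-menarche and post-menopausal females it continues: "surgically sterile, or using an effective method of contraception, or abstinence from at least 4 weeks prior to vaccination", with the condition running until at least 4 weeks after vaccination.
- **The exclusion.** Protocol 5.2.5, criterion 1, excludes anyone meeting this description: "Subject is pregnant, or lactating, or of childbearing potential". It then gives the same definition. The synopsis version reads "surgically sterile, or using an effective method of contraception or abstinence from at least 4 weeks prior to vaccination" and differs from the step 6 footnote by one comma.
- **A second use of the term.** Footnote d to criterion 1 says of a girl who reaches menarche during the study: "then she is to be considered as a woman of childbearing potential from that time forward". It makes no exception for contraception.

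**The concern.** The definition combines two things: whether a woman is physiologically able to conceive, and whether she is taking steps not to. Used in an exclusion criterion alone, that is clumsy but workable. Used in the testing rule as well, it takes out of the test the women for whom a test is informative, namely fertile women who enrol on the strength of contraception or abstinence.

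What is at stake is subject safety. Four of the six groups receive investigational formulations, and Protocol 5.1.2 says this "will be the first trial in humans to evaluate the different formulations of SP0173". The urine test is the only objective pregnancy check scheduled before vaccination. A site that omitted it for a woman on contraception would be following the protocol as written. With approximately 20 centres, the wording may also be read differently from site to site.

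**Working it through.** The plan states no figure on this point, so the check is one of logic. Take each category of female under the shared definition and ask whether step 6 requires the test and whether criterion 1 permits enrolment. Subjects who are pregnant or lactating are excluded in any case and are left out.

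| Category | Status under the definition | Test required at V01? | Can enrol under criterion 1? |
|---|---|---|---|
| Pre-menarche | Not of childbearing potential | No | Yes |
| At least a year past menopause | Not of childbearing potential | No | Yes |
| Surgically sterile | Not of childbearing potential | No | Yes |
| Fertile, on effective contraception or abstinent throughout the window | Not of childbearing potential | No | Yes |
| Fertile, neither of these | Of childbearing potential | Yes | No, whatever the result |

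No row has a yes in both of the last two columns, so the number of women both required to be tested and able to enrol is 0.

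Two further checks on the text:

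- *Does footnote d restore the test?* No. It changes a girl's status only if menarche occurs during the study, and the only scheduled pregnancy test is at V01.
- *Does the SAP widen the rule?* No. Table 3.2 repeats the protocol footnote and adds nothing.

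For scale only, consider the two younger age groups:

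- Planned adolescents and adults: 450 + 450 = 900.
- On investigational formulations (4 of 6 groups): 900 × 4/6 = 600. On licensed controls: 900 × 2/6 = 300.
- Assume half are female: 600 × 0.5 = 300.
- Assume 50% to 80% of those are fertile: 300 × 0.5 = 150 and 300 × 0.8 = 240.
- With a wider fertile share of 30% to 90%: 300 × 0.3 = 90 and 300 × 0.9 = 270.

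The documents give neither the female share nor the fertile share. These are counts of women outside the wording. They are not counts of women who went untested or were pregnant.

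**The case against.** The best reply is that the intent is plain. A negative result as a condition of enrolment makes sense only if tested women can enrol. Step 6 also comes after the eligibility check at step 4, so the women who reach it have already passed criterion 1. Read so as to have some effect, step 6 must mean fertile women on contraception or abstinent, and footnote d uses the term in that physiological sense. This is good evidence of what the sponsor meant. It does not change what the step 6 footnote tells a site, which is that a woman on contraception is not in the tested group.

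The second reply is that the gap is partly covered, and that stands. Protocol 5.2.12 confirms that "Pregnancy is an exclusion criterion for enrollment in this study", so a known pregnancy excludes whatever the testing rule says. Fertile enrollees must use contraception or abstain from at least 4 weeks before vaccination, and pregnancies arising during the study are followed to outcome. The formulations also share their antigenic components with a licensed vaccine (Protocol 1.2). These points lower the risk, but an unrecognised pregnancy is what a test finds and what an exclusion without a test can miss.

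Two narrower points are fair. The 90 to 270 range follows from assumed shares and measures no risk; the firm result is the empty set. The site Operating Guidelines, which are not available here, may instruct sites to test, and nothing in the documents shows that any site would skip it.

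**Conclusion.** The rule is wrong as written. Under the protocol's own definition, no woman is both eligible and required to have the V01 pregnancy test, and no other part of the protocol or SAP repairs this. The conclusion needs no assumption beyond the text. The illustrative 150 to 240 women on investigational formulations (90 to 270 on the wider assumption) rests on an assumed half-female enrolment and an assumed fertile share.

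The consequence is limited to subject safety and is partly mitigated. No endpoint, analysis set or sample-size figure changes. It should be corrected because a mandatory pre-vaccination safeguard has been written so that it binds on no one who is vaccinated.

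**What to change.** Separate physiology from behaviour:

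1. Define a woman of childbearing potential as post-menarche, not yet a year past menopause, and not surgically sterile.
2. Exclude such a woman only if she is not using effective contraception or abstinent from at least 4 weeks before to at least 4 weeks after vaccination. Keep pregnancy and lactation as exclusions in their own right.
3. Require a negative urine test before vaccination from every woman of childbearing potential.

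The essential edits are in three places: the synopsis exclusion criterion 1, the footnote to step 6 in Protocol 5.1.4, and criterion 1 in Protocol 5.2.5. Once the definition is physiological, step 6 and the schedule footnotes in the protocol and SAP work as they stand and need only a consistency check. Footnote d then agrees with the main definition.

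The cost is small. The test is already a scheduled V01 procedure. Measured against the literal text, the change adds one urine test per fertile enrollee; where sites already test these women, it adds nothing. Because it alters an eligibility definition on safety grounds, it would probably count as a substantial amendment needing ethics approval under Protocol 5.4. No analysis changes.
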